#### **Study Design**

We propose to conduct a dose escalation trial. We will test the tolerability to 10 g, 20 g, and 30 g of soy containing 4 g, 8 g, and 12 g of DF respectively. At each dose, eight subjects will incorporate the foods into their usual diet for one week. We will evaluate tolerability to each dose and measure fecal SCFA as a biomarker of compliance. Subjects who satisfy the eligibility criteria and express willingness to consume the study foods will be enrolled.

At baseline, weight and vital signs will be measured. Subjects will provide a stool sample collected within the last 48 hours and frozen in containers provided for the purpose. Part of the fecal samples will be archived for future analysis. The study dietitian will interview each subject in order to assess the subject's current intake. Based on this information, subjects will be counseled on incorporating the study foods in their diet with the appropriate fluid intake. Subjects will receive the study foods containing 4g DF/10g soy/day for one week and complete a tolerability questionnaire.

Subjects will consume the soft foods containing soy along with their regular diet for one week, and will be advised to return all used and unused containers at the end of the week. Compliance will be assessed from an interview with the subject and an evaluation of used and unused containers returned by subjects. Pre-intervention tests and measures will be repeated, and adverse events will be recorded. If a dose is tolerated, subjects will receive the next escalated dose for one week (8 g DF/20 g soy/day or 12 g DF/30 g soy/day). At the end of each subject's participation in the study, a fasting blood sample will be drawn for evaluation of CBC, and blood chemistry panel as safety markers.

The results of the present study will guide the design and implementation of a clinical trial to determine the effect of a low GI D+E program on insulin sensitivity and apathy in elderly subjects with obesity and insulin resistance. These results will be significant, in that they will potentially provide a cost-effective intervention that will substantially improve the health and quality of life for the growing number of elderly individuals with obesity who have developed insulin resistance and apathy.

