## HYPOTHESIS AND SPECIFIC AIMS

Edamame or green soybean in the pod has approximately four times more dietary fiber than soybean without the pod. The whole soy pod (soy), rich in phytonutrients, increases fecal fat and glucose excretion and the synthesis of short chain fatty acids in mice. The majority of the clinical and epidemiologic evidence supports the anti-depressive effects of diets high in soybeans. In previous controlled feeding and exercise studies, we found that a low GI D+E for one week (n = 32) or 12 weeks (n = 22) increases insulin sensitivity in older adults with obesity. These data form the basis of a proposal to test the hypothesis that insulin sensitivity mediates apathy in depression. No study to date has empirically tested this hypothesis. The success of the efficacy trial depends on a determination of the optimal dose of dietary fiber from soy that will be tolerated by the elderly. Therefore, the present study will determine the maximum tolerated dose of dietary fiber from soy. The results will inform the development of a randomized controlled trial (RCT) to test the efficacy of a low GI D+E program (with and without soy) to increase insulin sensitivity and reduce apathy in the elderly.

**Aim.** Determine the maximum tolerated dose of dietary fiber from soy in elderly subjects with obesity. This aim requires a dose escalation trial in the elderly with obesity. We will test the tolerability to soft foods including 10 g, 20 g, and 30 g of soy containing 4 g, 8 g, and 12 g of dietary fiber, respectively. At each dose, eight subjects will consume the foods for one week. We will evaluate tolerability to each dose and measure fecal short chain fatty acids as a biomarker of compliance with the intervention.

**Hypothesis:** Since this is a dose finding study there is no hypothesis for the maximum tolerated dose; however, fecal short chain fatty acids will increase with the dose.

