## RESEARCH DESIGN AND METHODS

To determine an acceptable dose of DF, we will conduct a dose escalation trial in eight elderly subjects with obesity and test the tolerability to soft foods containing 4 g, 8 g, and 12 g of DF/day from soy for one week at each dose. The soy contains approximately 39% DF. Therefore, subjects will consume soft foods containing 10 g, 20 g, and 30 g of soy/day to provide the required DF doses and the phytonutrients in soy. This clinical trial is patterned according to the National Cancer Institute's (NCI's) recommendation for dose escalation to determine toxicity to a drug. We are testing a food, and we know that relatively large doses of DF are tolerated if daily intake is divided into small portions throughout the day. However, we will evaluate tolerability to DF from soy, and measure fecal SCFA as a biomarker of compliance with the intervention. The maximum recommended starting dose (MRSD) for DF may be estimated at 4 g which added to average DF intake in the US of approximately 17g is not in excess of the recommended adequate intake of 25 - 38 g/day. The dose escalation scheme recommended for first-in-human trials is rapid dose escalation initially (MRSD x 2) until the estimated desirable dose (8 g) is reached and then at a more cautious escalation (e.g. MRSD x 1.5). Subjects will consume soft foods containing 4 g/day of DF from soy for one week, then proceed to 8 g/day for one week, followed by 12 g/day for one week, incorporated into their usual diet.

Adverse events will be recorded as they occur and collated for each week. Fecal SCFA and gastrointestinal (GI) symptoms will be evaluated at the end of each week (Figure 2).

[figure not shown]

Figure 2. Study schema

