## Study Subjects

This study will enroll 10 healthy adult male and female subjects. Subjects will be enrolled on the basis of the following eligibility criteria:

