## **SAMPLE SIZE AND ANALYSIS**

The primary objective of the study is to determine the maximum tolerated dose of DF. Six subjects at each dose are sufficient to detect tolerability. However, we will enroll 10 subjects to test each dose of DF from soy. Dose safety will be investigated by compiling by treatment (e.g. 4 g dose, 8 g dose, 12 g dose) a list of adverse events such as frequency of headaches, nausea, vomiting. For GI symptoms the scale is ranked as none (no symptoms), mild, moderate, and severe for each of four GI symptoms and the assessment of intensity is provided in the data safety monitoring plan. Moderate and severe ratings will be considered intolerance to the dose. Stool frequency of one to three/day, or three times/ per week is considered regular. Therefore, stool frequency of less than one and more than nine over a 72 hour period will be a consideration for determining intolerance. Stool consistency of Type three to five on the Bristol Stool Scale is considered normal. Any other rating will be considered in the determination of intolerance. To be considered intolerance, subjects must rate stool frequency and consistency as being of moderate to severe intensity.

According to the NCI convention for dose limiting toxicity to a drug, 1) if two out of three (66%) subjects are intolerant to the dose, the next lower dose is the maximum dose tested; and 2) if one out of three (33%) are intolerant to a dose, then that dose is considered the maximum tolerated dose. Therefore for a food, 1) if five out of eight (63%) are intolerant, we will adopt the next lower dose; and 2) if three out of eight (37%) are intolerant to a dose, then that dose will be taken as the maximum tolerated dose.

A mixed effect linear model will be used to estimate changes in the fecal SCFA while accounting for subject correlation across time using all available data. The outcome will be within subject changes over time.

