### Lifestyle intervention to reduce apathy in the elderly

**Brief Description of Intervention:** To determine an acceptable dose of dietary fiber from soy, a dose escalation trial in eight older subjects with obesity will be conducted. The tolerability to soft foods containing approximately 4 g, 8 g, and 12 g/day of dietary fiber (depending on the nutrition analysis of the soy flour) from 10g, 20g, and 30g of soy flour for one week at each dose will be assessed, and the maximum tolerated dose will be determined.

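### The plan enrols 10 subjects in two places and says eight in five others, and its only rule for the maximum tolerated dose is written out of eight, with no version for 10

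*Combined protocol and SAP*

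**What the plan says.** Two places give 10. Study Subjects: "This study will enroll 10 healthy adult male and female subjects". Sample Size and Analysis says that six per dose would suffice, then adds: "However, we will enroll 10 subjects to test each dose of DF from soy".

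Five places give eight:
- Abstract, Study Design: "At each dose, eight subjects will incorporate the foods into their usual diet for one week".
- Hypothesis and Specific Aims: "At each dose, eight subjects will consume the foods for one week".
- Research Design and Methods: "we will conduct a dose escalation trial in eight elderly subjects with obesity".
- Data safety monitoring plan, Brief Description of Intervention: "a dose escalation trial in eight older subjects with obesity will be conducted".
- Data safety monitoring plan, Brief Description of Project Design, where the number eating the study foods is again eight.

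Sample Size and Analysis starts from a convention for drugs (2 of 3, 66%: go down a dose; 1 of 3, 33%: this dose is the MTD) and adapts it to a food in two limbs: "if five out of eight (63%) are intolerant, we will adopt the next lower dose", and "if three out of eight (37%) are intolerant to a dose, then that dose will be taken as the maximum tolerated dose". Section 2.0 of the monitoring plan repeats the definition of intolerance in a subject but gives no cohort threshold. Section 3.2 has the investigator discuss each escalation with the Safety Officer and gives no number. Clinic Visits says that a participant who does not tolerate a dose is not advanced.

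**The concern.** The MTD is the primary objective, and these two limbs are the only numeric rule that produces it. If 10 subjects take a dose, the plan does not say how many intolerant subjects make that dose the MTD or send the study down a dose. Someone must then choose a conversion, possibly after seeing the data. With three doses 4 g apart, one changed decision moves the reported MTD by 4 g/day, and Hypothesis and Specific Aims says that the later efficacy trial depends on this result.

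There is also a gap at eight. The limbs name 5 of 8 and 3 of 8 without saying that they are minimums. Results of 6 to 8 of 8 can only sensibly mean going down a dose, but 4 of 8 falls between the two points and is not assigned.

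**Working it through.** **The plan's own figures.** 5/8 = 62.5% (printed 63%) and 3/8 = 37.5% (printed 37%). 2/3 = 66.7% (printed 66%) and 1/3 = 33.3% (printed 33%). All agree apart from rounding or truncation. No formula lies behind six, eight or 10, so there is no sample size calculation to reproduce.

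**Reading used.** Both limbs are taken as minimums: at or above the upper point, next lower dose; from the lower point up to it, MTD; below the lower point, escalate. At n = 8, the counts (3, 5) and the exact fractions (37.5%, 62.5%) then agree for every result from 0 to 8.

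**Conversions to n = 10.**
- Printed counts carried over: 3 and 5.
- Exact fractions as strict cut-offs: 0.375 × 10 = 3.75, so at least 4; 0.625 × 10 = 6.25, so at least 7.
- The same products rounded to the nearest subject: 4 and 6.
- The plan's own step from thirds, which at eight gives 8/3 = 2.67 → 3 and 16/3 = 5.33 → 5, gives at 10: 10/3 = 3.33 → 3 and 20/3 = 6.67 → 7.

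| Intolerant of 10 | Counts 3/5 | 4/7 | 4/6 | 3/7 |
|---|---|---|---|---|
| 0–2 | escalate | escalate | escalate | escalate |
| 3 | MTD | escalate | escalate | MTD |
| 4 | MTD | MTD | MTD | MTD |
| 5 | next lower | MTD | MTD | MTD |
| 6 | next lower | MTD | next lower | MTD |
| 7–10 | next lower | next lower | next lower | next lower |

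Against the carried-over counts, the strict percentages differ at 3, 5 and 6, the rounded percentages at 3 and 5, and the conversion from thirds at 5 and 6.

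**How often such a count arises.** The documents give no intolerance rate, so p is assumed. P(X = k) = C(10,k) p^k (1−p)^(10−k).

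| Outcome | p = 10% | p = 20% | p = 30% |
|---|---|---|---|
| X = 3 | 0.057 | 0.201 | 0.267 |
| X = 5 | 0.001 | 0.026 | 0.103 |
| X = 6 | 0.000 | 0.006 | 0.037 |
| 3 or 5 | 0.059 | 0.228 | 0.370 |
| 3, 5 or 6 | 0.059 | 0.233 | 0.407 |
| 5 or 6 | 0.002 | 0.032 | 0.140 |

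Sums use unrounded terms.

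**Where these figures apply.** They need all 10 at the dose, and only 4 g assures that. At 4 g there is no lower tested dose, so a next-lower-dose decision there has no action. All 10 reach 8 g only if none was intolerant at 4 g: 0.9^10 = 35% if the 4 g rate is 10%, and 0.8^10 = 11% if it is 20%. With nine evaluable, the counts and exact fractions still differ at 3 of 9 (33.3%) and 5 of 9 (55.6%).

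**The case against.** The strongest reply is that the rule is proportional. It is derived from thirds, a percentage stands beside every fraction, and few readers would apply bare counts of 3 and 5 to a denominator of 10. That largely stands: percentage scaling is the more natural reading. But the plan does not say so, and scaling alone does not settle the integers, since 4/7, 4/6 and 3/7 can all be defended.

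A second reply is that 10 are enrolled so that eight complete. The verbs lend it some support: both places with 10 speak of enrolling, while most of those with eight speak of eating the foods. But no attrition or replacement allowance is given, Sample Size and Analysis puts the 10 at each dose, and Withdrawal of Subjects expresses a wish to analyse everyone enrolled.

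Third, the monitoring plan expects these doses to be tolerated. At a rate of 10% the ambiguity is about 6%. The same plan expects gastrointestinal symptoms, and a moderate rating counts as intolerance, so 20% or 30% cannot be excluded, but nothing in the documents establishes either.

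A reader might infer that the rule gives wrong decisions at 3, 5 and 6 of 10. The documents do not support that: it requires the less natural reading, and the conflict at 6 disappears if 6.25 is rounded to the nearest subject, while the conflict at 3 disappears under the conversion from thirds.

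**Conclusion.** Wrong as written: the enrolment number and the primary decision rule do not match, and no text reconciles them. The rule has no form for 10, leaves 4 of 8 unassigned, and does not say whether count or percentage governs.

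At a dose that all 10 receive, and at assumed rates of 10%, 20% and 30%, the chance of 3 or 5 intolerant is about 6%, 23% and 37%; adding 6 makes it 6%, 23% and 41%. These measure how often the text would leave room for two answers under a count-versus-percentage comparison. They are not probabilities of a wrong MTD. If the conversion from thirds were adopted, the overlap with bare counts would be at 5 or 6 only: 0.2%, 3% and 14%.

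It would also be too strong to read this as a risk to participants. An intolerant participant is not advanced whichever number is used, so the effect is on the reported MTD. The point should be fixed, in proportion to a small food-tolerability pilot.

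**What to change.** 1. State one sample size throughout, or say that 10 are enrolled to obtain eight evaluable, and what applies if nine or 10 complete.
2. Before dosing, write the rule as exhaustive bands for the number actually evaluable. For example: below 37.5% intolerant, escalate; 37.5% to below 62.5%, this dose is the MTD; 62.5% or more, next lower dose. Use the exact fractions, because 5 of 8 is 62.5% and would miss a literal 63% cut-off.
3. Print the integers as minimums: at least 3 and at least 5 of 8. For 10, at least 4 and at least 7 matches these bands; 4 and 6, or 3 and 7, are also defensible if the sponsor prefers them and words the bands to match.
4. State the denominator at 8 g and 12 g, since intolerant subjects are not advanced. One option is everyone who began dosing, with those stopped for intolerance counted as intolerant at higher doses.
5. Say what follows if the upper limb is met at 4 g, where there is no lower tested dose.

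The cost is protocol wording only: no extra subjects, visits or procedures.

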#### **CLINIC VISITS**

Subjects will complete one screening visit. There will be four study visits **unless a participant is intolerant to a dose and cannot be advanced to the next higher dose.**

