**Table 1. Schedule of Assessments for Dose Response Study**

Procedure	Screening 1	Baseline	Visit 1	Visit 2	Visit 3
PBRC Outpatient Unit					
Infomed Consent	X				
Height	X				
Weight, and Vital Signs	X	X	X	X	X
Chemistry 15 Panel/CBC	X				X*
Medical History Questionnaire	X				
MMSE and GDS-15	X				
Adverse Events**			X	X	X
Medications	X	X	X	X	X
Tolerability Questionnaire**		X	X	X	X
Food Dispensation		X	X	X	
Nutrition Counseling**		X	X	X	
Compliance with Study Foods			X	X	X
Fecal Sample (SCFA)***		X	X	X	X
Fecal Sample (Archives)	X	X	X	X	

\* Or at a prior visit if the dose is not tolerated

\*\* By phone call on day prior to the study visit.

\*\*\*Measured at Scioto Biosciences

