### **Visit 1 (Week 1, 1 hour)**

Assessment of adverse events, completion of the tolerability questionnaire, and nutrition counseling will be completed by phone on the day prior to the visit to avoid unnecessary food preparations in the event that the participant does not tolerate the dose. Subjects will report to the clinic for the visit and the following tests and measurements will be performed:

- Collection of fecal sample.
- Measurement of weight and vital signs.
- Recording of changes in medications.
- Dispensation of study foods.
- Assessment of compliance by metabolic kitchen staff.

- Dispensation of stool collection kit.

A blood draw for CBC/Chemistry panel will be performed if participants are not being advanced to the next dose. Participants will be advised to report after a ten hour fast.

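### The maximum tolerated dose is set by counts out of eight at each dose, but intolerant subjects are not advanced and no rule says how they count at higher doses

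*Combined protocol and SAP*

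**What the plan says.** SAMPLE SIZE AND ANALYSIS converts an oncology convention stated in thirds into counts out of eight. Five of eight intolerant means that the next lower dose is adopted. For the other trigger, "if three out of eight (37%) are intolerant to a dose, then that dose will be taken as the maximum tolerated dose".

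The design sections assume a full group of eight at every dose. Study Design states: "At each dose, eight subjects will incorporate the foods into their usual diet for one week". HYPOTHESIS AND SPECIFIC AIMS repeats it: "At each dose, eight subjects will consume the foods for one week".

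The doses are nevertheless given in sequence to the same people. RESEARCH DESIGN AND METHODS states: "Subjects will consume soft foods containing 4 g/day of DF from soy for one week, then proceed to 8 g/day for one week". Individuals stop on intolerance: CLINIC VISITS plans four study visits "unless a participant is intolerant to a dose and cannot be advanced to the next higher dose". The schedule carries this through. The Table 1 footnote moves the closing blood panel: "Or at a prior visit if the dose is not tolerated". Visit 1 and Visit 2 both provide for early leavers: "A blood draw for CBC/Chemistry panel will be performed if participants are not being advanced to the next dose".

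Nothing in the available text says whether a subject stopped at one dose counts as intolerant at the next, leaves the denominator, or is replaced. Section 2.0 of the monitoring plan repeats the definition of intolerance without a counting rule. Section 3.2 leaves each escalation to a discussion between the investigator and the Safety Officer, also without one.

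**The concern.** Eight subjects at each dose and no advancement after intolerance cannot both hold for one cohort once anyone stops. The subjects left at 8 g and 12 g are those who tolerated what came before. If only they are counted, each early failure disappears from the later tallies and the higher doses look better tolerated than they were among the people who started.

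The maximum tolerated dose is the primary result, and the plan says that it will inform the later efficacy trial. That trial's participants will not have been selected for tolerating 4 g and 8 g first. The same count also bears on whether the remaining subjects in this study go up a dose.

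**Working it through.** **The plan's own percentages.** 5/8 = 62.5% (stated 63%), 3/8 = 37.5% (stated 37%), 2/3 = 66.7% (stated 66%), 1/3 = 33.3% (stated 33%). All agree up to rounding or truncation.

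**Two ways of counting.** Let eight start, with x, y and z new intolerances at 4, 8 and 12 g.

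- On-dose: x of 8, y of (8 − x), z of (8 − x − y).
- Cumulative: x, x + y and x + y + z, each of 8.

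**Direction.** As counts, y ≤ x + y and z ≤ x + y + z. As proportions, y/(8 − x) ≤ (x + y)/8 is equivalent to 0 ≤ x(8 − x − y), which always holds; replacing x by x + y gives the same result at 12 g. So the on-dose count names a dose equal to or higher than the cumulative count.

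**An example that needs no assumed rate: x, y, z = 0, 2, 3.**

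| Dose | On-dose | Cumulative |
|---|---|---|
| 4 g | 0 of 8 | 0 of 8 |
| 8 g | 2 of 8 | 2 of 8 |
| 12 g | 3 of 6 | 5 of 8 |
| Dose named | 12 g (three intolerant) | 8 g (five of eight) |

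No trigger is met before 12 g, so it does not matter whether a trigger halts dosing. The counts at 12 g fall exactly on stated triggers, so the handling of four does not matter either. The on-dose share, 3/6 = 50%, matches neither stated percentage.

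**How often the counts disagree.** The documents give no intolerance rates, so the rates below are assumptions. With cumulative intolerance c4, c8 and c12 by each dose, and r = 8 − x − y − z,

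P(x, y, z) = 8!/(x! y! z! r!) × c4^x × (c8 − c4)^y × (c12 − c8)^z × (1 − c12)^r.

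This is summed over all patterns in which the two counts name different doses. The trigger counts are applied as stated: four is treated as three, more than five as five, and if no trigger is met 12 g is named. Column 2 stops at the first trigger. Column 3 lets dosing continue past three of eight, so only five or more stops it.

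| Assumed c4/c8/c12 | Stop at first trigger | Three of eight does not stop dosing |
|---|---|---|
| 2/5/10% | 0.4% | under 0.1% |
| 5/10/20% | 3% | 1% |
| 10/20/30% | 14% | 6% |
| 10/25/40% | 23% | 17% |
| 10/30/50% | 33% | 34% |
| 20/40/60% | 44% | 56% |

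In every row the on-dose count names the higher dose; the reverse has probability 0. The chance that all eight starters reach 12 g, ignoring any group stop, is (1 − c8)^8. With c8 = 10% that is 0.90^8 = 43%, so a denominator below eight is likely even at modest rates.

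**The case against.** The strongest reply is that the text already favours one reading. Intolerance is defined by a moderate or severe rating of a dose, and a subject who never took 12 g has no rating at 12 g. That stands. A reader might infer that the plan offers two equally supported counts; it does not, and the cumulative count is a proposed addition. But the literal reading is the one that drops early failures, and it leaves three of six without a rule.

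Second, tolerance is expected. Section 1.1 of the monitoring plan cites other fibers as well tolerated at 15 g/day and expects 4, 8 and 12 g to be tolerated. Section 1.2 defines moderate as interfering with everyday activities, which is a fairly high bar. This supports the lower rows of assumed rates, and the higher ones have no basis in the documents.

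Third, more than eight are recruited: "However, we will enroll 10 subjects to test each dose of DF from soy". A reader might take the extra two as replacements. The text does not say so, two would not cover three or more stops, and replacement would not settle how stopped subjects count. The Safety Officer's involvement, and the ease of reading both counts from so few subjects, help but supply no rule.

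Other patterns look like proof but are weaker. With 2, 1 and 1 new intolerances, one might say that the cumulative count stops at 8 g. That requires three of eight to halt dosing, which the plan does not state. If dosing continues, the cumulative count reaches four of eight at 12 g; with four treated as three, both counts name 12 g. With 2, 2 and 1, the on-dose share at 8 g is 2/6 = 33%, the one-in-three fraction that the plan itself cites, so an investigator could name 8 g under either count.

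**Conclusion.** The concern holds as a gap in the rule that produces the primary result. Taken literally, the rule counts only subjects on the dose and can name 12 g when five of eight starters have become intolerant. The direction is certain: on-dose counting never names a lower dose than cumulative counting.

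The size is not known. With dosing stopped at the first trigger and four treated as three, disagreement runs from about 0.4% at assumed rates of 2/5/10% to 44% at 20/40/60%. If three of eight does not stop dosing, it runs from about 1% at 5/10/20% to 56% at 20/40/60%. A reader might infer that the study will probably overstate the tolerated dose. The documents do not support that: they give no rates, and their stated expectation of tolerability points to the low end.

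The missing action for four of eight, and the mismatch between eight in the triggers and ten enrolled, are separate points.

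**What to change.** Add to SAMPLE SIZE AND ANALYSIS:

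> A subject stopped for intolerance at a lower dose counts as intolerant at every higher dose. The denominator is all subjects who started 4 g, less those who left for reasons other than intolerance. The 3/8 and 5/8 triggers are applied to this proportion.

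Report the on-dose and cumulative counts at each dose, so that the designers of the later trial can see both.

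The cost is protocol wording only, with no added subjects, visits or doses. The downside is that the cumulative count is conservative. The Nutrition Counseling text expects gastrointestinal symptoms to resolve, so some stopped subjects might later have tolerated more, and the named dose could be too low. Because intolerant subjects are not advanced, this cannot be observed under either count.
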